1.4.8.2. Neurodevelopment

Neurodevelopment will be assessed using the Rapid Neurodevelopmental Assessment (RNDA), administered when the child is awake and there should be no distraction and prompting allowed from parents while performing the assessment. While administering the assessment the response elicited from the infant will be recorded.

The Rapid Neurodevelopmental Assessment (RNDA) tool is a reliable and valid developmental assessment tool for use by multidisciplinary professionals in developing country to assess the neurodevelopmental status of children from 0-24 months(47). The tool has been a useful to identify neurodevelopmental impairment (NDI) in resource limited settings where there is lack of trained professionals to identify children with neurodevelopmental impairments. It assesses developmental domains such as primitive reflexes (0 to <1 month), gross motor, fine motor, vision, hearing, speech, cognition, behavior and seizures. It helps to identify impairments in these developmental domains and categorizes into three degrees of impairments which are mild, moderate and severe impairment.

1.4.8.3. Compliance

Parent compliance will be measured by the ability of the parent to correctly demonstrate the home program activity when they come for the follow up visit. In addition, parental compliance will be measured by quantifying the amount of time spent with the infant

performing the intervention at home, number of intervention sessions attended, the number of enrolment and outcome assessment at the end of the study.

[figure not shown]

Figure 3: Procedure

1.4.8.4 Intervention

Intervention group

The intervention that will be used for this study will be adapted and modified for the Bhutanese cultural context, from supporting play exploration and early development intervention (SPEEDI) (43). The intervention is designed to improve the developmental outcome of preterm infants who are at risk of developmental disabilities. SPEEDI uses the combined therapist and parent delivered intervention to increase opportunities for developmentally appropriate social, cognitive and motor play without excessive parental and financial burden. SPEEDI blends the synactive theory of development and action perception theory to enhance developmental outcomes in high risk infants. The original version of SPEEDI consist of two phases where first phase is the intervention provided to the infants during the stay in NICU and phase two provided post discharge from NICU. For this study the infants will receive the interventions adapted from SPEEDI both as an outpatient based.

The Phase I of the original version of SPEEDI consist of parent therapist collaborative sessions to understand infant cues, readiness for interaction, developmental support and stressors, ideas to promote interaction and development and watching the videos which is provided during the stay in NICU. However, this phase I intervention will be provided post discharge from the NICU at 40 weeks. The main objective of making parents watch these videos would be to help parents interact with their infant and perform the activities at home since most of the parents would be anxious and not know how to interact with their infant. The Phase II from the original version consisted of home visit to provide the intervention post discharge from NICU. It consists of therapist guiding the parents to perform play-based activities at home with their infants and these activities can be performed as a part of daily activities with their infants especially during feeding, bathing and changing diapers. There are 5 main activities which the parents must perform with their infant at home. The activities are broken down into three stages that become progressively challenging over time. For this study purpose the phase II intervention will be provided at the hospital where the parent will need to bring their infant to the hospital and the 5 main activities will be broken down into two stages. During the monthly visit the principal researcher will assess and decide the infant's ability to progress the activity from stage 1(easy) to Stage 2(hard). If the infant is found to be not ready to progress to the next stage, they will continue with the same activity. The primary caretaker will be given activity booklet which will contain pictures, simple text and log to record daily

activities. To perform the play- based activities the primary caretaker will be asked to use toy within their natural home environment since the intervention does not require any specific or sophisticated toys.

Intervention	40 weeks	1 month	2 months
Activities	
 • Watching videos to understand cue-based interaction with the infant. • Introduce the activities that the parent can complete at home to promote midline and tracking of toys and faces 	
 • Watching people and toy • Tummy time • Holding head up • Kicking • Toy play 	
 • Watching people and toy • Tummy time • Holding head up • Kicking • Toy play
Duration	20 mins/day	20 mins/day	20 mins/day
Frequency	5 days /week	5 days /week	5 days /week

Figure 4: Intervention Program

Activity	Stage 1	Stage 2
Activity1 – Looking at people and toys (4 minutes)	
 • Looking at people with support in supine • In side lying and swaddled 	
 • Tracking of caregiver in supine.
Activity 2- Tummy time (4 minutes)	
 • Tummy time on the caregiver’s chest 	
 • Tummy time on the floor
Activity 3- Holding head up (4 minutes)	
 • Head control with help from caregiver. • Head control by swaddling the baby. 	
 • Head control with less support from caregiver, unswaddled.
Activity 4- Kicking (4 minutes)	
 • Kicking with swaddle to support to support the arms. 	
 • Kicking with arms and legs free to move with slight support under the hips.
Activity 5- Toy play (4 minutes)	
 • With use of external support to bring hands and legs in middle. 	
 • Toy play without external support and variety of position such as supine and side lying.

Figure 5: Activity Description

The intervention will be provided as an outpatient based at JDWNRH by the principal researcher. It will require the parents to come to the hospital every month for the assessments and interventions. The parents will be called every week to ensure that they have no problem with the activities until the infant is 3 months of corrected age. The principal researcher will review and assess if the parents are performing the intervention correctly with the infant during the monthly visit. The parents in the intervention group will be advised not to share the activities and any information related to the intervention to other parents of preterm infants whom they might know.

They will be given appointment for assessment at different day or time and the information regarding the enrollment will be kept confidential.

Standard care group

Standard care group will include education regarding early development which is present in the mother and child handbook and which is currently practiced. The standard care group will also be required to visit the clinic monthly and assessment will be performed monthly until the infant is 3 months of corrected age. During the monthly visit parents will be asked to report the amount of time spend with their infant performing the activity.

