1.4.5 Sample size

Sample size calculation will be based on the study by Dusing et al(43). According to the study they found a significant difference in motor performance of infants born preterm who received physical therapist delivered intervention compared to the usual care group. The effect size from the study was Cohen's d of 1.29 for TIMP z- score. Using this data, the total sample size of 22 was obtained using G power program version 3.1. However, with 20% drop out rate a total of 28 infants born preterm would be required with 14 in each group.

[figure not shown]

Figure 2: G power

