1.4.9 Data Analysis

The researcher assistant who performed the randomization will register all neonatal data, discharge variables and the follow-up data, during the appointments. Motor performance of the infant will be assessed using TIMP at 40 weeks, 1 month, 2 months and 3 months of corrected age and neurodevelopment will be assessed using RNDA. Scores of TIMP items and items from RNDA will be transformed from categorical scale to a continuous scale. The Rasch Unidimensional Measurement Model (RUMM) will be used for this process. The number of sessions and amount of time spent performing the intervention will be recorded and analyzed. All the variables will have double data entry.

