1.4.10 Statistical Analysis

Statistical analysis will be performed using Statistical Package for Social Sciences (IBM SPSS statistics for windows, version 28). Shapiro Wilk test will be used to test for normality of data. Descriptive statistics will be used to analyze patient's demographic data. To investigate the effect of physical therapist intervention on motor performance two-way mixed ANOVA will be performed. To investigate the effect of physical therapy intervention on neurodevelopment two-way mixed ANOVA will be performed. The level of significance will be set at a p-value < 0.05.

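### The TIMP outcome is not referenced to age and is analysed by nominal visit, so age at test adds noise and any mean age difference between arms would be read as a motor difference

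*Combined protocol and SAP*

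**What the plan says.** Section 1.4.8 (Measurement) places assessments at 40 weeks postmenstrual age and at 1, 2 and 3 months corrected age. No permitted interval is given around any of them. The only timing tolerance is in 1.4.8.1, which allows 24 hours to finish a split TIMP session; that is not a visit window.

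Section 1.4.9 (Data Analysis) defines the analysed scores: "Scores of TIMP items and items from RNDA will be transformed from categorical scale to a continuous scale", using a Rasch model. No age norm is mentioned there. A z-score appears only in 1.4.5 (Sample size), where the trial is sized on a "d of 1.29 for TIMP z- score".

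Section 1.4.6 treats time as four nominal visits, and 1.4.10 (Statistical Analysis) specifies a two-way mixed ANOVA for TIMP and for RNDA. Neither section uses actual age at test.

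On contact with families, 1.4.8.4 says under the intervention group: "The parents will be called every week to ensure that they have no problem with the activities", continuing to 3 months corrected age. Under standard care it says: "The standard care group will also be required to visit the clinic monthly and assessment will be performed monthly". No calls are described for that group. Section 1.4.7 mentions a link between the team and the parents of both groups, as an enrolment strategy and without a schedule.

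**The concern.** Section 1.4.8.1 describes the TIMP as covering 34 weeks postmenstrual age to 4 months corrected age, a span over which infants gain motor skill quickly. A Rasch conversion makes the score continuous but does not reference it to age. If an infant due at 3 months is tested late, the analysis records the score simply as the 3-month value.

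This has two consequences.

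- **Noise.** If test ages scatter equally in both arms, the extra variation enters the error term and costs power in a trial of 28 infants.
- **Bias.** If mean test age differs between arms, the difference appears as a group effect. If it changes from visit to visit, it appears as a group-by-time interaction. Randomisation does not prevent this, because attendance timing arises after allocation. Assessor blinding does not prevent it either, because the score is correct for the infant's true age.

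The weekly calls are one way in which attendance could come to differ between arms. Older infants in standard care would mask a benefit of SPEEDI; younger ones would exaggerate it.

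**Working it through.** **1. The plan's own figure.** Inputs from 1.4.5 and 1.4.10: d = 1.29 and significance at 0.05. Power and sidedness are not in the readable text (the G*Power figure is not shown), so 80% and two-sided are assumed. A two-sample t-test by the noncentral t distribution needs 11 per arm, 22 in total, with actual power 82.1%. Dropout: 22 / (1 − 0.20) = 27.5, rounded up to 28, or 14 per arm. The stated 22 and 28 reproduce, and this point does not alter them.

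**2. Bias from a mean age difference.** Let g be the rise in score per week, in between-infant SDs at a fixed age, and w the difference in mean test age between arms in weeks. With roughly linear growth over a few days:

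shift = g × w

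The documents give neither g nor w. Assumed ranges are g = 0.1 to 0.7 and w = 0.5 or 1.

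- w = 0.5: 0.1 × 0.5 = 0.05 SD, up to 0.7 × 0.5 = 0.35 SD
- w = 1: 0.1 × 1 = 0.1 SD, up to 0.7 × 1 = 0.7 SD

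To see what this does to a single-visit comparison with no true effect, enter the shift as the noncentrality (shift × √(n/2), n per arm) of the two-sided 5% t-test:

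| Shift (SD) | Rejection rate, 11 per arm | Rejection rate, 14 per arm |
|---|---|---|
| 0.05 | 5.1% | 5.2% |
| 0.1 | 5.6% | 5.7% |
| 0.2 | 7.3% | 8.0% |
| 0.35 | 12.2% | 14.5% |
| 0.7 | 34.6% | 43.0% |

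**3. What a one-week gap requires.** w is a difference between arm means. One infant 14 days late among 14 moves the arm mean by 14/14 = 1 day. A shift of 7 days needs, for example, 7 of 14 infants each 14 days late (7 × 14 / 14 = 7).

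**4. Noise with equal punctuality.** Let test age scatter with SD s weeks in both arms (s = 1 assumed). The SD of the score becomes √(1 + (g × s)²), so the standardised effect falls to 1.29 / √(1 + (g × s)²):

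- g = 0.1: 1.29 / √1.01 = 1.28; power at 11 per arm 81.7%
- g = 0.4: 1.29 / √1.16 = 1.20; power 76.2%
- g = 0.7: 1.29 / √1.49 = 1.06; power 65.5%

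These figures carry the d of 1.29 over to the Rasch scale for illustration only. It was stated for the z-score, so the comparison is loose.

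**The case against.** The strongest reply is that nothing in the documents shows that punctuality will differ by arm. A reader might infer from 1.4.8.4 that SPEEDI families are reminded of their visits every week and control families never, so that the comparison is biased. The text does not support that. The calls are to help with the activities and are nowhere called appointment reminders. The standard care text is silent on calls rather than ruling out contact. Section 1.4.7 foresees a link with parents in both groups, and both groups must attend monthly. Weekly support is also part of the package being tested, so unequal contact is not itself a defect. No direction of bias can be predicted. All of this stands.

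It is also fair that the low end of the range is negligible: shifts of 0.05 to 0.1 SD leave the rejection rate near 5% to 6%. One or two late families would not produce a one-week gap.

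Finally, gestational age is recorded (1.4.8) and follow-up data are registered at the appointments (1.4.9), so age at test can probably be worked out afterwards. That holds only if dates are kept, and the plan does not say that they are. An adjustment chosen after the data are seen is also weaker than one stated in advance.

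What survives is narrower. The planned analysis cannot separate age at test from motor performance, and it neither limits, detects nor corrects an age difference if one occurs. The noise does not depend on the calls at all.

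**Conclusion.** The point holds as a conditional weakness with an inexpensive remedy. An outcome that is not referenced to age, analysed by nominal visit, lets age at test add noise and would read a mean age difference between arms as a motor difference. On assumed growth of 0.1 to 0.7 SD per week, the shift is about 0.05 to 0.35 SD for a half-week gap and about 0.1 to 0.7 SD for a one-week gap. Both inputs are assumptions. So is the rise of the Rasch score with age, although the age span that the TIMP covers makes it hard to doubt. The z-score in 1.4.5 is taken to be age-referenced, which the plan does not spell out.

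The documents do not establish that the weekly calls will cause such a gap, or in which direction. They are one possible route, and the case for the change does not rest on them.

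**What to change.** **In 1.4.8:** record corrected age in days at every TIMP and RNDA assessment. Set the same target window around each age for both arms. Give both arms the same appointment reminder before each follow-up visit, separate from the SPEEDI support calls, which stay as they are.

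**In 1.4.10:** choose one of two analyses in advance.

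- Compare arms with a linear mixed model containing group, visit and group by visit, with exact corrected age at test as a visit-level covariate. The standard two-way mixed ANOVA does not accommodate a covariate that changes from visit to visit, so the model itself must change.
- Or, for the TIMP, analyse the age-referenced z-score on which the trial was sized. RNDA would still need the age covariate.

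Keep out-of-window visits in the analysis. The window alone is not enough: an interval of, say, 7 days either side would still allow arm means of +3.5 and −3.5 days, a one-week gap. Using exact age is the essential part.

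**Cost:** a mixed model in place of the mixed ANOVA, one recorded variable, and about three short reminder calls per family (3 × 28 = 84 at most). The sample size and the content of SPEEDI do not change.

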1.4.7 Data Collection

The study will be conducted after seeking ethical approval from Institutional Review Board (IRB), Khesar Gyalpo University of Medical Sciences of Bhutan (KGUMBS). The data will be collected at pediatric physiotherapy unit, JDWNRH. Preterm infants referred for high risk follow up clinic at Pediatric Physiotherapy Unit that evaluates neurodevelopmental outcome will be recruited. Oral and written information will be given to parents of the preterm babies fulfilling the inclusion criteria. Parents will be informed regarding the objectives, procedures, risk and benefits of the study. Informed consent will be taken from the parents prior to the study by the principal investigator. Strategies to achieve adequate participant enrolment to reach target sample size will be, establish a link between

the research team and mother and father of each of the subjects included, regardless of the group allocated since randomization.

Randomization will be performed by blindly drawing the slip from the container which will have equal numbers of same size and shape slips and will be performed by the research assistant who will not be responsible for any intervention nor outcome assessment. After randomization the infants in the control group will receive standard care and the infants in the intervention group will receive modified SPEEDI. The principal researcher will provide the modified SPEEDI. The research assistants shall be physical therapist or physical therapy assistants and occupational therapist who has over 2 years of experience in working with pediatric population and will be blinded to the group allocation since they will assess the outcome. These research assistants will be trained to use the measurement tools by the principal researcher. As the study participants are preterm infants, caution will be taken to avoid thermal stress to these infants by keeping the data collection room in pediatric physiotherapy unit warm. During the study process if there are amendments to the study protocol, the information shall be communicated with the IRB and the co-investigators of the study.

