1.4.8 Measurement

Prior to the assessment of motor performance and neurodevelopment, demographic details such as gestational age, length of stay in the hospital and medical diagnosis will be recorded. The measurement will be taken at 40 weeks of post menstrual age, 1 month, 2 months and 3 months of corrected age by the research assistants who will be blinded to group assignment.

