1.4.8.1 Motor performance

Motor performance will be assessed using The Test of Infant Motor Performance (TIMP) version 5.1, administered when the child is awake (Brazelton state 3,4 or 5). The infant should wear minimal clothing as possible. Testing will be performed on a firm surface with no distractions. No more than 3 trials will be allowed for each elicited item. If the infant gets fussy and irritable during the process of assessment, breaks can be taken in between the assessment and if the parents are not comfortable with the procedure the parents will have every right to withdraw and discontinue their infant's participation from the study. However, if the parent consents to continue the assessment, items that remain during the first session shall be

completed in second session within 24 hours so that it assessor does not have to redo the whole assessment again.

The Test of Infant Motor Performance (TIMP) was developed to assess functional motor performance in infants from 34 weeks postmenstrual age (PMA) through 4 months corrected age. The TIMP is a 42- item assessment with 13 dichotomous items scored based on observation of spontaneous movement and 29 elicited items with 4 to 7-point rating scales based on handling of the infant in a variety of positions in space. The test takes 20-35 min to administer and score with variation based on age and tolerance of the infant and the experience of the tester. It has been described as one of the best tools to discriminate between age-appropriate and delayed motor performance in preterm and term infants, and to predict later motor development. The TIMP is a valid and reliable tool developed to detect typical and atypical performance in preterm infants and evaluate the effect of an intervention on the infant motor performance(44-46). The assessment tool has been also used in multiple clinical trials to evaluate the effectiveness of therapy intervention.

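### The rule that assessment appointments be on a different day or time can tie clinic slot, and possibly assessor, to arm, and nothing in the plan balances them.

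*Combined protocol and SAP*

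**What the plan says.** The intervention-group part of section 1.4.8.4 has parents attend monthly: "It will require the parents to come to the hospital every month for the assessments and interventions". It then turns to contamination: "The parents in the intervention group will be advised not to share the activities and any information related to the intervention to other parents". The next sentence, the last before the standard-care text, begins: "They will be given appointment for assessment at different day or time". It ends with a promise that enrolment details stay confidential.

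The standard-care text sets the same frequency but no booking rule: "The standard care group will also be required to visit the clinic monthly and assessment will be performed monthly".

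Section 1.4.7 describes the assessors as a mixed group: "The research assistants shall be physical therapist or physical therapy assistants and occupational therapist who has over 2 years of experience". They are blinded to allocation and trained on the tools by the principal researcher. No assignment of assessors to infants, visits or arms is described. Section 1.4.8 gives both arms the same target ages: "The measurement will be taken at 40 weeks of post menstrual age, 1 month, 2 months and 3 months of corrected age". Section 1.4.8.1 standardises the conditions of the TIMP (infant state, surface, absence of distractions). Section 1.4.10 plans a two-way mixed ANOVA, and section 1.4.6 lists group and time as the only independent variables.

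**The concern.** The booking sentence governs the outcome assessment, not only the teaching session. A site could reasonably follow it by seeing intervention families in one set of slots and standard-care families in another. Anything that varies by slot, such as how settled infants are at that hour or who is on duty to score, could then differ systematically between arms.

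Randomisation protects the comparison at entry. It does not protect it from a difference in how the outcome is measured afterwards. If slot and arm coincide completely, no analysis can separate them. If they coincide partly, adjustment is possible only if slot and assessor were recorded, and the plan does not ask for that.

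There is also a second route. An assessor who notices that certain slots belong to one arm is no longer blinded, and the TIMP and RNDA both depend on the examiner's judgement.

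Controlling contamination requires that families do not meet. It does not require that arms be separated.

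**Working it through.** **1. The plan's own figure.** Section 1.4.5 gives Cohen's d = 1.29, 22 evaluable infants, and 28 enrolled after 20% dropout (14 per arm). The readable text states neither power nor sidedness; I assume 80% and two-sided 5%. For a two-sample t-test the noncentrality is d × √(n/2) = 1.29 × √(11/2) = 3.03 on 20 degrees of freedom. Power is 82.1% with 11 per arm, and 11 is the smallest number per arm that reaches 80%. Total 22; 22 / 0.8 = 27.5, rounded up to 28. The stated figures reproduce, and this point does not change them.

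**2. What the text supports.**

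- *Who is meant.* The sentence sits under the intervention-group heading and follows one whose subject is the parents in that group. The standard-care text has no counterpart. Arm-specific booking is the natural reading.
- *Different from what.* Not stated. Booking every family separately would also satisfy the words.
- *Balance.* Nothing in sections 1.4.7 to 1.4.10 spreads days, times or assessors across arms.
- *Model.* There is no term for assessor, day or time of day.

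**3. How a slot effect enters the estimate.** Let δ be the score difference, in SD, between two kinds of slot. Let p₁ and p₀ be the shares of assessments made in the first kind in the intervention and standard-care arms. The bias in the group difference is δ × (p₁ − p₀). With arms fully separated, p₁ − p₀ = 1 and the bias is δ. With arms interleaved evenly, p₁ − p₀ = 0 and so is the bias.

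**4. Illustration.** The documents contain no value for δ, so the range below is an assumption. With true effect zero and full alignment, the noncentrality is δ × √(n/2). The rejection rate is that of a two-sided 5% t-test.

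| Assumed shift (SD) | Share of 1.29 | 11 per arm | 14 per arm |
|---|---|---|---|
| 0 | 0% | 5.0% | 5.0% |
| 0.1 | 7.8% | 5.6% | 5.8% |
| 0.2 | 15.5% | 7.3% | 8.0% |
| 0.3 | 23.3% | 10.3% | 11.9% |
| 0.5 | 38.8% | 20.1% | 24.7% |

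For example, 0.5 × √(11/2) = 1.17 gives 20.1%. Alignment need not be complete: a 0.2 SD slot effect with p₁ − p₀ = 0.5 is a bias of 0.1 SD and a rate of 5.6%. The direction is also unknown; a shift against the intervention would hide benefit.

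**5. Link to the planned analysis.** The t-test is a stand-in for the mixed ANOVA. A shift equal at all four visits loads on the group main effect and leaves the group-by-time interaction alone. A shift that starts after baseline loads on both. The protocol does not say which term decides the trial, so the consequence for its conclusion cannot be fixed more closely.

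**The case against.** The strongest reply is that the sentence may only mean separate booking for each family. It does not say what the slot differs from, it requires a different day *or* time rather than both, and it is joined to a promise of confidentiality that would suit any participant. Any two non-overlapping slots on the same morning would comply. Visits are set by each infant's own age, the TIMP takes 20 to 35 minutes per infant, and 28 infants would reach their target ages on scattered dates. No arm-specific clinic is described. Blinding, common training, a warm room and the required infant state all limit how much a slot could matter.

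Most of this stands as a limit on certainty and size. It does not remove the point. The safeguards reduce variation, but none balances slots or assessors across arms, and nothing in the readable text prevents booking by arm.

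A reader might go further in two ways that the documents do not support.

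- *That assessors are tied to arm.* No roster appears. Section 1.4.7 describes one pool of assessors, and a mix of professions does not mean that profession follows arm. The link is possible only if staffing happens to differ by slot.
- *That the arms would be tested at different ages.* Both arms share the same target ages, and a different day or hour does not imply a different mean age. The lack of a stated visit window applies to both arms and is a separate matter.

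**Conclusion.** The concern holds as a risk created by the wording, not as a demonstrated bias. On its natural reading, section 1.4.8.4 separates the arms at outcome assessment. Arm can then become tied to slot and possibly to assessor, blinding can be weakened, and the planned ANOVA cannot undo it.

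The size is unknown. The range of about 7% to 20% false positives rests on four assumptions: a shift of 0.2 to 0.5 SD, complete alignment with arm, no true effect with 11 per arm, and a single t-test in place of the mixed ANOVA. A reader might take those rates as the trial's expected error; they show only what full separation could do. If individual booking was intended, the trial loses nothing by saying so. The change is worth making before enrolment because it is cheap and because unrecorded slots cannot be reconstructed later.

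**What to change.** Replace the booking sentence in section 1.4.8.4 with:

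> Each family in both arms is given its own non-overlapping appointment. Appointments for the two arms are interleaved over the same clinic days, times of day and assessors. The booking list is held by someone already on the team who does not assess outcomes.

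Keep the confidentiality clause. The research assistant who draws the randomisation slips is one candidate to hold the list, since section 1.4.7 gives that person no part in intervention or outcome assessment.

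Add to section 1.4.8 that assessor, date, time and exact corrected age are recorded at every visit, and to section 1.4.10 that they are reported by arm. Imbalance would then be visible.

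The cost is slightly more scheduling effort for 28 infants and four extra fields per visit. Sample size stays at 22 evaluable and 28 enrolled, with no added staff or visits. Families are still kept apart, so contamination control is preserved.
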